### 2.8.1 Adverse Event Reporting and Data and Safety Monitoring Plan

The investigators will monitor subjects for evidence of adverse events. All adverse events will be reported to the IRB following the IRB reporting policies and procedures and followed until satisfactory resolution.

### 3. HUMAN SUBJECTS RESEARCH

#### 3.1 Protection of Human Subjects

The study will be conducted with strict adherence to Washington University Institutional Review Board protocol and consent form approval. An American Board of Anesthesiology board-certified and GCP-certified anesthesiologist with experience in conducting clinical studies will lead the study. Safety and privacy of study participants will be safeguarded. Patient confidentiality will be maintained through de-identification of personal health information. Identity and linking information will be locked cabinet within the principal investigator's (PI) office, which is locked outside of business hours. Electronic data will be password encrypted on secure servers.

### 3.1.1 Indemnity

Washington University School of Medicine is responsible for any non-negligent damage incurred as a result of participating in the RCC II Trial. This indemnity is renewed on an annual basis. Washington University School of Medicine assures that it will continue renewal of the indemnity for the duration of the trial.

# 3.1.2 Ethics and Dissemination

The trial investigators will be responsible for all major decisions regarding changes to the protocol. The committee will communicate these changes to the IRB and appropriate parties. The final trial dataset is the property of the investigative team and shall not be shared without permission from the principal investigator. Dissemination plans include presentations at local, national and international scientific conferences. Every effort will be made to publish results of the RCC II trial in a peer-reviewed journal. Dissemination of results to study participants and their family members will be available upon request. Updates and results of the study will be available to the public at clinicaltrials.gov.

### 3.2 Sources of Materials

Patients will receive remuneration of \$100 per session after the titration visit (Visit 2-7), or \$600 for completion of the study. Patients who undergo an MRI scan will receive an additional \$50 for their time. There will be no cost for involvement.

# 3.3 Recruitment and Informed Consent

Screening and enrollment of subjects will occur according to the protocol-defined inclusion and exclusion criteria.

### 3.4 Potential Benefits of the Proposed Research to the Participant and Others

This study will be the first to explore and elaborate how a seizure in the form of ECT (combined with an induction dose of intravenous anesthesia) impacts consciousness and cognition following termination of the seizure. The time course and sequence of reconstitution of consciousness and cognition will also be clarified. This investigation will yield novel insights into an excitatory impairment of consciousness, which has not previously been studied with a controlled, experimental design.

Candidates for ECT are refractory to multiple medical modalities. These patients may benefit from a greater understanding of the relationship between anesthetics and ECT on recovery of cognitive function and efficacy for depression treatment.

This study may benefit the patient directly. Ketamine may improve the efficacy of ECT and recovery of cognitive function following ECT. The patient may benefit from the additional EEG monitoring in the post-ictal period during which non-convulsive status epilepticus is rarely manifested.

### 3.5 Inclusion of Women

Efforts will be made to enroll patients regardless of gender.

### 3.6 Inclusion of Minorities

All studies in the Department of Anesthesiology encourage the participation of minorities in research. Our minority recruiting typically matches the demographic composition of the Washington University patient population (30% white, 60% Black, 6 % Hispanic, 4% Asian).

### 3.7 Inclusion of Children

No children will be enrolled in this study.

#### Appendices:

#### 1. Study Day (each experimental treatment day Visit 2-Visit 7)

#### **Pre-Treatment:**

An appropriately fitted 64-channel (n=15-20 subjects) EEG headcap (Electrical Geodesics, Inc. Eugene OR) will be affixed to the scalp. The actual placement of EEG electrodes might vary, depending on the requirements for ECT. Electrical impedances on each channel will be confirmed to be under 100kOhms/channel. Subjects will complete a baseline round of neurocognitive testing with ongoing EEG recordings, as well as 3D-CAM (3D-Confusion Assessment Method), Self-Assessment Manikin, PROMIS-CAT (Patient Reported Outcomes Measurement Information Systems - Computer Adaptive Testing) for depression, and the Scale of Suicidal Ideation (Table 1).

#### **During Treatment:**

Upon completion of the neurocognitive battery, the subjects will be pre-oxygenated by mask and anesthesia will be induced by either ketamine, 2 mg/kg or standard of care anesthetic, depending on group assignment. The induction agent will be slowly titrated until there is loss of responsiveness and eyelash reflex, which is current practice for ECT. During this time, an audio loop command will be issued every 30 seconds asking the subject to randomly squeeze their left or right hand. Loss of consciousness (LOC) will be recorded as the first time when a subject fails to respond to two consecutive commands. Antiemetic prophylaxis will be administered as clinically indicated. During the sessions that subjects receive ECT, other drugs will also be administered according to current practice and as clinically indicated. ECT will be conducted according to current standard practice. EEG will be acquired after the ECT charge has been delivered or continuously for non-ECT ketamine sessions. After the ECT has been concluded (or after the induction dose of ketamine has been administered), the patient will remain in the treatment room for subsequent testing and EEG recording.

### **Post-treatment:**

Recovery of consciousness (ROC) will be defined as the first time at which subjects correctly responded to two consecutive audio loop commands. At this time, defined as t = 0 minutes, the subject will begin the neurocognitive battery of tests followed by a brief resting period. Neurocognitive testing will be repeated at t= 30, 60, and 90 minutes following emergence while the 3D-CAM will be completed at time 0 and every hour (Table 1) until the patient is scored negative for delirium. Each battery of neurocognitive testing will take

approximately 15-20 minutes to complete. During the rest period, EEG recording will occur with 5 minutes eyes open and 5 minutes eyes closed. At the 90 timepoint patients will not only complete the COGNITION cognitive test but also the 3D-CAM (if positive for delirium at t=60, PROMIS-CAT, Self-Assessment Manikin, and a questionnaire regarding patients' subjectivity of whether they received ECT. Subjects will be permitted to take a brief break to use the restroom and eat or drink, as necessary. Subjects will be discharged according to standard post-anesthesia care unit discharge criteria upon completing the last neurocognitive test battery. A study site coordinator will contact each subject within 24 hours of the study day to document any adverse events.

Assessment	Baseline (Pre-ECT)	Time 0	Time 30	Time 60	Time 90
COGNITION Neurocognitive Testing	х	Х	Х	Х	Х
3D-CAM - Delirium (3D- Confusion Assessment Method)	х	х		х	х
PROMIS-CAT - (Computer Adaptive Testing for depression)	Х				х
Mood Self-Assessment Manikin - mood	Х				х
Scale of Suicidal Ideation	х				
Assessment for Blinding Quality					х

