anesthesia will be induced with ketamine, approximately 2 mg/kg, or standard of care. Following bolus of the induction agent, loss of responsiveness and evelash reflex will be confirmed. Loss of consciousness will be recorded as the first time when a subject fails to correctly respond to the command. Care adherent to the ASA guidelines will be performed regardless of treatment session. For sessions with ECT, pre-stimulation hyperventilation and assisted ventilation will also be performed. Central seizure duration will be assessed from bilateral fronto-mastoid EEG by the psychiatry team. Peripheral seizure duration will be determined through monitoring of tonic-clonic activity (Fink and Johnson 1982). During the sessions that subjects receive ECT, other drugs will also be administered according to current practice and as clinically indicated. The return of eye opening will be assessed every 30 seconds and defined for the initial time at which the patient opens his eves to verbal command. The ability to extend the thumb to verbal command ("thumbs up") will be assayed every 30 seconds. Return of responsiveness to auditory command will be defined as the first time at which the patient has squeeze his correct hand the number of times instructed via auditory commands. At this time, defined as t = 0 minutes, the subject will begin a series of cognitive and behavioral assessments, which are repeated every 30 minutes up to two hours after return of responsiveness. Patients will be permitted to take brief breaks to use the restroom and eat or drink, as necessary. At the conclusion of each treatment session, depression testing (PROMIS-CAT) and mood assessment (Self-Assessment Manikin) will be performed to assess for early improvements in mood. To assess blinding quality, the patient will be asked their impression of whether they received ECT that day. They will be discharged according to standard post-anesthesia care unit discharge criteria upon completing the last neurocognitive test battery. A study site coordinator will contact each subject within 24 hours of the study day to assess and document any adverse events.

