#### **2.4.7.1 Outcomes** (Further details on instruments are provided in appendices)

#### Primary and Secondary Outcomes

Primary outcomes include: the temporal recovery profiles for cognitive task performance, as measured using the Cognition assessment battery (Basner, Savitt et al. 2015); times for the return of responsiveness to auditory command; and the presence of delirium, evaluated through the 3-Minute Diagnostic Assessment for CAM-defined delirium (3D-CAM)(Marcantonio, Ngo et al. 2014).

Secondary outcome measures based on the EEG will include definitions of the seizures by standard techniques using both expert reader interpretation and quantitative techniques (Haider, Esteller et al. 2016). Central seizure duration will be visually determined by clinician evaluation of the frontal-mastoid bipolar EEG ictal complexes. Additional measures will be calculated from windowed analyses of the high-density EEG: power spectral measures of the interval between anesthetic induction to delivery of ECT stimulus charge; the seizure envelope for 1-12 Hz EEG power; peak-to-peak amplitude, calculated from the difference in maximum and minimum voltages within 300 millisecond time; periodicity of epileptiform discharges; inter-hemispheric symmetry of seizure discharges; intra- and inter-hemispheric coherence. When possible, these measures and power spectral estimates will be derived different phase of the ictal waveforms(Gerst, Enderie et al. 1982). The following postictal EEG measures will be assessed: duration of postictal EEG suppression; power spectral parameters flanking the return of responsiveness to verbal command; power spectral parameters from eyes open and closed epochs, including assessments of the posterior dominant rhythm. Spatiotemporal analyses will also focus on the propagation of EEG signatures during the ictal and early postictal period.

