### **Delirium Assessment (3D-CAM)**

The 3D-CAM is a delirium assessment tool based on the full Confusion Assessment Method (CAM) interview. The 3D-CAM takes approximately 3 minutes to complete. In order for a patient to be positive for delirium they must present 3 of the 4 features including acute onset, inattention, altered level of conscious and/or disorganized thinking.

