20. Did the patient's speech/thinking fluctuate during the interview, for	IS PRESENT?
example, patient spoke slowly for a while, then sped up?	1 – No 2 - Yes
	1

CAM Summary – FEATURES 1-4

Coding for features 1 -4 (0)NO (1)YES
 1. Acute Onset and Fluctuating Course - Code 'Yes' if any of the items 8,
9, 10, 18,19 and 20 are incorrect/present
 2. Inattention - Code 'Yes' if any of the items 4,5,6,7, 16 and 17 are
incorrect/present
 3. Disorganized Thinking - Code 'Yes' if any of the items 1, 2, 3, 13, 14 and
15 are incorrect/present
 4. Altered Level of Consciousness - Code 'Yes' if any of the items 11 and 12
are present
 
 
Disorganized Thinking - Code 'Yes' if any of the items 1, 2, 3, 13, 14 and 15 are incorrect/present
 
Altered Level of Consciousness - Code 'Yes' if any of the items 11 and 12
 

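### The 3D-CAM schedule for a primary outcome is inconsistent, and the text's stop-at-first-negative rule would leave later delirium in a session unrecorded

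*Combined protocol and SAP*

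**What the plan says.** Section 2.4.7.1 lists among the primary outcomes "the presence of delirium, evaluated through the 3-Minute Diagnostic Assessment for CAM-defined delirium (3D-CAM". Section 2.5.1 models the effect of treatment on it, and section 2.5.2 relates its incidence to delayed recovery in every cognitive domain (Aim 3 in section 2.2).

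The rating times appear in three places:

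- Appendix 1, Post-treatment, text: "the 3D-CAM will be completed at time 0 and every hour (Table 1) until the patient is scored negative for delirium". The same paragraph says that at 90 minutes patients complete not only the cognitive battery "but also the 3D-CAM (if positive for delirium at t=60", so that rating is conditional as well.
- Appendix 1, Table 1: the 3D-CAM row is marked at baseline, 0, 60 and 90 minutes, with no condition or footnote.
- Section 2.3.8, Experimental Treatment Visits: from return of responsiveness the patient begins "a series of cognitive and behavioral assessments, which are repeated every 30 minutes up to two hours after return of responsiveness". The 3D-CAM is not named there and no stopping rule is given.

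The plan does not say how time points after a negative score are to be coded or analysed.

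**The concern.** The two sentences in Appendix 1 agree with each other, so the stopping rule is not a slip of wording: a session negative at time 0 has no further delirium rating. The instrument's first feature, required for a positive score, is "Acute Onset and Fluctuating Course", so it is not obvious that one negative rating soon after emergence closes the question.

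Three things are at stake. First, a change from negative to positive within a session cannot be seen, so the assumption that it does not happen cannot be tested with this trial's data. Second, how long a session is watched depends on the outcome being measured. Third, section 2.5.3 relates EEG power to 3D-CAM scores; under the text rule, the 60- and 90-minute EEG and cognitive data of a session negative at time 0 have no paired delirium rating.

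The inconsistency also leaves staff to choose a schedule. Section 2.3.6 says that the study and clinician teams know the treatment at each session, so ad hoc choices about repeat ratings could differ by arm.

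**Working it through.** The plan states no delirium rate and no power calculation for delirium, so there is no figure to reproduce. The first step is to compare the schedules.

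| Source | 0 min | 30 | 60 | 90 | 120 |
|---|---|---|---|---|---|
| Appendix 1 text, hourly clause | yes | no | if positive at 0 | no | if still positive |
| Appendix 1 text, 90-minute sentence | | | | if positive at 60 | |
| Table 1 | yes | no | yes | yes | not listed |
| Section 2.3.8 (3D-CAM not named) | yes | yes | yes | yes | yes |

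No single schedule satisfies all four rows.

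**Number of ratings.** Six experimental sessions for 15-20 patients give 90-120 sessions. Table 1 gives 3 post-treatment ratings per session, so 270-360. Taking the text as ratings at 0, 60 and 90 minutes with its conditions, the expected number per session is 1 + p0 + p0 × s. Here p0 is the proportion positive at time 0 and s the proportion of those still positive at 60 minutes. Both are assumptions. For p0 I use 5-12%, the rate of postictal agitation and disorientation in section 2.1.2. This is a rate per patient after ECT, not a 3D-CAM rate per session, and serves only as a rough proxy. With s = 25-50%:

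- low end: 1 + 0.05 + 0.05 × 0.25 = 1.0625, which is 35% of 3;
- high end: 1 + 0.12 + 0.12 × 0.50 = 1.18, which is 39% of 3.

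With p0 = 50% the share is 54-58%.

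**Sessions missed.** Let q be the assumed proportion of sessions negative at time 0 that would be positive at 60 or 90 minutes. Missed sessions = sessions × (1 − p0) × q. Missed share of all delirium sessions = (1 − p0)q / [p0 + (1 − p0)q].

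| q (assumed) | Missed, of 90-120 sessions, p0 = 5-12% | Share of delirium sessions missed |
|---|---|---|
| 0 | 0 | 0 |
| 1% | 0.8-1.1 | 7-16% |
| 2% | 1.6-2.3 | 13-28% |
| 5% | 4.0-5.7 | 27-49% |
| 10% | 7.9-11.4 | 42-66% |

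For example, at q = 2% the lower count is 90 × 0.88 × 0.02 = 1.6 and the upper is 120 × 0.95 × 0.02 = 2.3. With p0 = 50% and q = 1-10% the missed share falls to 1-9%.

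**Difference between arms.** If q is the same in every arm, each arm misses (1 − p0)q. For arms with p0 of 5% and 12% and q = 10%, that is 9.5 against 8.8 percentage points, a difference of 0.7. For an extreme assumed pair, p0 of 10% and 50%, the difference is 9 − 5 = 4 points at q = 10% and 4.5 − 2.5 = 2 points at q = 5%.

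**The case against.** A reader might infer that later delirium is never observed in this trial, that incidence is therefore underestimated, and that the arms are affected unequally. The documents do not support stating any of these as fact.

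- Non-observation holds only if the text overrides Table 1. If the table governs, later delirium is seen at 60 and 90 minutes. The text cites the table at the point of the rule, so the table can also be read as a maximum schedule with the text as its condition. That reading removes the conflict over conditions. It does not reconcile an hourly interval with a 90-minute rating, and it leaves the stopping rule in force.
- The fluctuation argument leans on a feature label. Items 18-20 of the instrument ask about change during the interview and items 8-10 about the past day. Neither shows that patients negative at emergence become positive an hour later. Section 2.1.2 says that agitation and disorientation may last 1-2 hours, which concerns persistence, and the rule does follow a positive session until its first negative rating.
- The outcome is presence of delirium. A session positive at time 0 is already counted, so longer observation adds nothing to its incidence. With equal late onset, the arms differ only slightly.
- Aim 3 can be addressed with one present/absent value per session; the plan does not commit to modelling delirium over time.
- Two hours in section 2.3.8 may simply mark the end of the 90-minute block: 15-20 minutes of testing plus 10 minutes of resting EEG would end at 115-120 minutes.

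These points limit the claim about bias. They do not remove the inconsistency or the fact that, under the text rule, a negative-to-positive change cannot be recorded.

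**Conclusion.** The point holds in a conditional form. It is established that the protocol gives irreconcilable 3D-CAM schedules for a primary outcome and that the text rule makes follow-up depend on the outcome. If that rule is followed, a session negative at time 0 has one post-treatment rating, and any later onset in it is lost. Relapse after a first negative rating is lost too, although a session already positive still counts as delirium present.

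The size of any understatement is unknown. It is zero if late onset does not occur. In the illustration it ranges from about one session to eleven, and this rests entirely on assumed values of p0 and q. Differential bias between arms is likely small unless late onset itself differs by arm, on which the documents are silent. The study is described as exploratory (section 2.5), so this does not undermine the design, but it should be corrected because the remedy is specific and cheap.

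**What to change.** 1. In Appendix 1, Post-treatment, replace "the 3D-CAM will be completed at time 0 and every hour (Table 1) until the patient is scored negative for delirium" with a statement that the 3D-CAM is done at 0, 60 and 90 minutes in every session, as in Table 1.
2. In the same paragraph, delete the condition on the 90-minute rating (being positive at 60 minutes).
3. Align section 2.3.8 with this schedule, naming the 3D-CAM and its last rating time. Removing the stopping rule alone would leave both the hourly wording and the two-hour schedule unreconciled.
4. In section 2.4.7.1, define the primary outcome as any positive post-treatment 3D-CAM in the session.

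If the stopping rule is to be kept, the consistent alternative is to define the outcome as delirium up to the first negative rating, say so in Table 1, and state how later time points are handled.

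The cost is small: "The 3D-CAM takes approximately 3 minutes to complete", so at most 2 × 3 = 6 extra minutes per session, or 36 minutes over six sessions, in slots that Table 1 already lists and while patients are still present for the 90-minute battery. Timing at 60 minutes is tight: 15-20 minutes of testing plus 10 minutes of resting EEG makes 25-30 minutes, and a further 3 makes 28-33 against a 30-minute interval. The time-0 block already carries the same load, so the order of tasks should be fixed for both. The 30-minute point would still have no paired delirium rating, as in Table 1 now.

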### Table 1: Assessment at Each Experimental ECT Treatment (Visit 2-Visit 7):

### 2. Description of Assessments:

### Neurocognitive testing (COGNITION battery)

This battery for individualized neurocognitive assessment of fatigue has been tested in the context of sleep deprivation and is administered via a laptop. The effects of ECT and/or an induction dose of an intravenous general anesthetic (ketamine or etomidate) on all the tests below have not previously been well characterized.

During administration, the order will be pseudorandomized, with a full complement given at each testing block. Additionally, the first test for each block will be repeated at the end to address temporal order within the block.

#### Motor Praxis Test (MPT)

The motor praxis test (MPT) measures sensory motor speed and fluidity. Participants are presented with a square box that, once clicked with a track pad mouse, shrinks and moves to a different location on the computer screen. Participants must click the box each time it re-appears as rapidly as possible. It is expected that the accuracy for the MPT will be close to 100%. Therefore, the standard score for this test is determined solely based on the speed at which the subject is able to click each square. Previous studies have shown that sensorimotor function performance declines with sleep deprivation. The Motor Praxis task allows for multiple measures of sensorimotor function in less than 1 minute.

### Psychomotor Vigilance Test (PVT)

The psychomotor vigilance test (PVT) measures sustained attention by recording reaction time to visual stimuli that are presented at random intervals. During the PVT, subjects are instructed to respond to a small red counter that appears at unpredictable intervals and reports time elapsed in milliseconds by clicking the space bar as soon as the counter appeared. This task is time limited as any response time greater than 500 milliseconds is recorded as a lapse or error of omission. The standard score for the PVT is based on response time and false starts. Originally, the PVT was designed for administration during 10-minute sessions. However, a shorter, modified PVT that remains sensitive to acute total sleep deprivation and chronic partial sleep deprivation was developed. Therefore, the PVT component of each neurocognitive battery in this study will be 3 minutes in duration. An advantage of using this task is that PVT is unaffected by learning and aptitude.

